In addition to establishing transcriptomic changes between targeted visits (e.g., Steroid Initiation vs. Steroid Assessments, before and after treatment), we will also examine the trajectory of gene expression changes among different study outcome groups across 25+ weeks of standard-of-care treatment as delineated in the protocol (up to seven scheduled sample visits) in a single analysis using WTS data from all STS samples, potentially revealing the regulatory pathways that govern disease and response/non-response to treatment across samples. To do this, we will use a linear mixed model based on normalized data to predict gene expression as a function of visit, outcome group, and their interaction (with a participant-specific random intercept). This model will enable us to identify differences in expression trajectories among outcome groups. Children and adults, and lesional and non-lesional skin will be analyzed separately.

Determining whether genetic variation that regulates skin gene expression is associated with AD disease [EO #15]

To identify genetic variants that may determine skin gene and endotype expression in different outcome groups, we will use imputed genome-wide genotype data (obtained as detailed in [Section 9.3](#)) and the WTS expression data to perform a cis-eQTL analysis. The eQTL analysis will be performed separately for children and adults, lesional and non-lesional skin, different visits, and different outcome groups. We will perform a meta-analysis of the test statistics for different sample groups. The final output will include a list of general skin eQTLs and eQTLs that are specific to different outcome groups.

To put the eQTLs discovered in the context of the AD endotypes, we will examine whether endotype genes contain significant eQTLs and determine whether eQTLs are harbored in genes that are enriched in cell types that define particular AD endotypes (based on the scRNA-seq data). Additionally, we will perform eQTL analyses separately for the most common endotype groups (i.e., for endotype-high individuals within endotypes with $n > 50$ high individuals). These analyses will identify genetic variants that affect gene expression specifically in AD endotype groups, which should be enriched for endotype genetic risk variants.

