13.7 Sample Size Considerations

13.7.1 Statistical power for study analyses

The study will enroll 600 participants in total, including: 300 adults with AD, 100 non-AD adults, 150 children with AD, and 50 non-AD children. Of the 450 AD participants, approximately 390 will be dupilumab-naïve. Dupilumab-naïve participant enrollment will be targeted to achieve approximately two thirds moderate-to-severe participants (moderate-to-severe AD adults = 160, moderate-to-severe AD children = 80) and one third mild participants (mild AD adults = 100, mild AD children = 50). We will target approximately 60 long-term dupilumab participants who are currently being treated with dupilumab and have received dupilumab for ≥ 4 months (20 children, 40 adults). These long-term dupilumab participants will be excluded from the primary objective and secondary objective #1.

Based on these population targets, we make several additional assumptions regarding sizes for the study outcome groups. Among the dupilumab-naïve AD participants, only those who fail topical steroid treatment will initiate dupilumab treatment. Currently, we project a 50% failure rate for topical steroids among the dupilumab-naïve moderate-to-severe participants and a 5% failure for the dupilumab-naïve mild AD participants ([Brunner et al, 2016](#)). Therefore, we anticipate topical steroid non-response in 85 adult AD participants and 43 children with AD, who will go on to receive dupilumab. Finally, of these dupilumab-naïve participants who receive dupilumab

during the study, we expect that approximately 40% will achieve $EASI \leq 7$, per the following reference ([Beck et al, 2014](#)).

This sample size powers the primary comparison of type 2-high inflammation status by baseline severity group at 80%. Specific details about power and sample size for the primary and secondary objectives are below.

Power analysis for Primary Objective

The primary objective for the study is to determine if the type 2-high non-lesional skin (skin tape) endotype is associated with current mild versus moderate-to-severe AD disease.

[figure not shown]

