Adults	AD vs. non-AD	260	100	1.38	1.44
	Mild AD vs. non-AD	100	100	1.48	1.55
	Moderate-to-severe AD vs. non-AD	160	100	1.42	1.48
	Moderate-to-severe AD vs. Mild AD	160	100	1.42	1.48
Children	AD vs. non-AD	130	50	1.58	1.67
	Mild AD vs. non-AD	50	50	1.74	1.85
	Moderate-to-severe AD vs. non-AD	80	50	1.64	1.74
	Moderate-to-severe AD vs. Mild AD	80	50	1.64	1.74

Additionally, Figure 13.7.1.2 displays a range of power scenarios for these comparisons of interest.

Figure 13.7.1.2 Power curves for differential expression analyses in SO1. A) Assuming target sample sizes. B) Assuming sample sizes after 20% dropout by end of study.

Note that SO1 will assess differences in gene expression at both Day 7 and End of Study (Day 168-224).

Power analysis for Secondary Objective #2

SO2 is as follows: to determine how gene expression in the skin (skin tape) changes over time among the study outcome groups: (1) topical steroid responders, (2) dupilumab responders, (3) dupilumab non-responders, (4) non-AD, and (5) long-term dupilumab participants.

[figure not shown]
Anticipated group sample sizes are based on the targeted population sample sizes and assumed treatment response rates described in [Section 13.7.1](#). The method for power calculation and underlying assumptions (gene expression CV, alpha, etc.) were identical to those used for SO1. Based on these assumptions, we have 80% power to detect statistically significant fold changes in gene expression between the study start and end points for the groups and fold changes listed in Table 13.7.1.3. Again, we calculated power for both our target samples sizes as well as for the case of 20% dropout by end of study.

Table 13.7.1.3 Power justification for Secondary Objective #2 in adults and children

Population	Study outcome group	Sample size	Minimum detectable fold change at 80% power	
			Assuming target sample size	Assuming 20% dropout
Adults	Topical steroid responders	175	1.34	1.39
	Dupilumab responders	34	1.95	2.11
	Dupilumab non-responders	51	1.73	1.84
	Non-AD	100	1.48	1.55
	Long-term dupilumab	40	1.85	1.99
Children	Topical steroid responders	87	1.52	1.60
	Dupilumab responders	17	2.57	2.88
	Dupilumab non-responders	26	2.15	2.35
	Non-AD	50	1.74	1.85
	Long-term dupilumab	20	2.39	2.65

Additionally, Figure 13.7.1.3 displays a range of power scenarios for these expression changes of interest.

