2.3 Exploratory objectives

Not covered in this SAP, please refer to a separate Exploratory SAP.

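### EO15 promises eQTLs specific to an outcome group or endotype, but the supplied documents state no between-group test that would support the word

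*Protocol*

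**What the plan says.** Protocol section 13.4.4, EO #15, sets out three steps.

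- The split: "The eQTL analysis will be performed separately for children and adults, lesional and non-lesional skin, different visits, and different outcome groups".
- The combination: "We will perform a meta-analysis of the test statistics for different sample groups". The method, any heterogeneity measure and any threshold are not given.
- The output: "The final output will include a list of general skin eQTLs and eQTLs that are specific to different outcome groups". The term *specific* is not defined.

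The next paragraph adds eQTL runs restricted to endotype-high individuals, for endotypes with more than 50 such people. It says these runs will find variants acting specifically in endotype groups. No run in endotype-low participants, and no comparison with them, is described.

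No power or sample size is given for EO15. Projected group sizes come from the SO2 power table (Protocol section 13.7.1, Table 13.7.1.3). The largest adult row reads "Topical steroid responders 175 1.34 1.39", that is, the group, its size, and the detectable fold change without and with 20% dropout.

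On exploratory objectives SAP section 2.3 says only: "Not covered in this SAP, please refer to a separate Exploratory SAP".

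**The concern.** To call an eQTL specific to group A is to claim that its effect differs between A and the other groups. A set of within-group tests does not establish that. An eQTL with the same effect everywhere will tend to reach significance in the large groups and miss it in the small ones, so a list built on within-group detection partly follows sample size.

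The endotype paragraph makes this more than missing wording: there, detection within endotype-high individuals is itself presented as showing specificity. Elsewhere the plan tests differences directly. SO2 and EO14 use a visit-by-outcome-group interaction, and EO11 and EO12 a visit-by-response interaction. At stake is that a list labelled by outcome group would be read as the genetics of treatment response, and an endotype list as endotype-specific risk, without evidence of a difference.

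**Working it through.** **1. Reproduce the group sizes.** The protocol says "we project a 50% failure rate for topical steroids among the dupilumab-naïve moderate-to-severe participants" and "a 5% failure for the dupilumab-naïve mild AD participants", and "we anticipate topical steroid non-response in 85 adult AD participants and 43 children with AD".

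- Adults: 0.50×160 + 0.05×100 = 85 steroid failures; 260 − 85 = 175 steroid responders. At 40% dupilumab response, 0.4×85 = 34 responders and 51 non-responders. Non-AD is 100 and long-term dupilumab 40.
- Children: 0.50×80 + 0.05×50 = 42.5, rounded to 43. The table gives 87, 17, 26, 50 and 20.

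The table's fold changes also reproduce with exp{√[(z₁₋α/₂ + z₀.₈)² × (1/10 + 0.4²) × 2/n]} and α = 0.05/10,000, taken as two-sided. For n=175: (4.565 + 0.842)² × 0.26 × 2/175 = 0.0869, and exp(√0.0869) = 1.34. For n=34 the result is 1.95. Both match.

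**2. Effect of group size on the statistic.** For one common effect, the expected z scales with √n. Between 175 and 34 adults the ratio is √(175/34) = 2.27.

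**3. What a rule of significance in exactly one group would do to a shared eQTL.** The documents give no such rule, no eQTL threshold and no effect size, so all three are assumptions here. Suppose the eQTL explains the same share R² of expression variance in every group, and use two-sided p<1e-5 (z = 4.417). Then

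power(n) = Φ(√[n·R²/(1−R²)] − 4.417).

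Example, R²=0.15, so R²/(1−R²) = 0.1765:

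- n=175: Φ(5.557 − 4.417) = 87%
- n=100: Φ(4.201 − 4.417) = 41%
- n=51: Φ(3.000 − 4.417) = 8%
- n=40: Φ(2.657 − 4.417) = 4%
- n=34: Φ(2.449 − 4.417) = 2%

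The groups contain different people, so the results multiply. P(any) = 1 − 0.1271×0.5856×0.9218×0.9608×0.9754 = 0.936. P(exactly one) = 0.497, of which 0.442 falls on steroid responders. Then 0.497/0.936 = 53%, and 0.442/0.497 = 89% of those calls land in the largest group.

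The same calculation over a range, as the chance of significance in exactly one group given any detection:

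| R² | Adults, p<1e-5 | Adults, p<1e-4 | Children, p<1e-5 |
|---|---|---|---|
| 0.10 | 85% | 66% | 98% |
| 0.15 | 53% | 27% | 92% |
| 0.20 | 19% | 5.5% | 79% |
| 0.25 | 4% | 0.5% | 58% |
| 0.30 | 0.3% | <0.1% | 33% |

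For lesional skin the non-AD group drops out, because its schedule in Appendix A has non-lesional samples only. With the four remaining adult groups at p<1e-5, the column becomes 96%, 87%, 67%, 41% and 18%.

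**4. Check by another method.** Noncentral-F power at α = 5e-6 (the SO1/SO2 threshold, borrowed) gives, for five adult groups, 92% at R²=0.10, 71% at 0.15, 38% at 0.20 and 2.5% at 0.30.

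**5. Effect of adding a between-group test.** A 4,000-run simulation used five adult groups, identical effects, assumed allele frequency 0.3 and α = 5e-6. Under the exactly-one-group rule, the share of detected shared eQTLs labelled specific was 72%, 39% and 3% at R² = 0.15, 0.20 and 0.30. Also requiring a Cochran Q heterogeneity p<0.05 cut this to 4.3%, 1.7% and 0.1%.

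**The case against.** The strongest reply is that the plan does not stop at separate analyses. A meta-analysis across sample groups comes directly before the promised list, and depending on its method it could separate shared from differing effects. The detail may also sit in the Exploratory SAP. Both points stand. A reader might infer that the plan treats non-significance in a small group as absence of effect, or that the list will mainly rank groups by size. The documents do not support either reading: they state no rule for *specific* at all, and the rule modelled above is a hypothesis.

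The meta-analysis sentence still does not close the gap. It speaks of combining test statistics, which mix effect size with sample size. Pooling them serves the general list; it does not say how the specific list is formed. Nor does it reach the endotype paragraph, where no comparison is described.

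It is also fair that the problem fades quickly for strong effects in adults' non-lesional skin, that the group sizes are SO2 projections, that the meta-analysis may combine visits while the calculation uses one sample per person, and that a joint interaction model is not the only remedy.

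**Conclusion.** The concern holds as a gap in definition and method. In the supplied documents, claims of specificity to an outcome group or endotype rest on no stated between-group comparison.

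The size is conditional. If specificity were read from per-group significance at p<1e-5, an eQTL shared equally by all five adult groups would appear in only one of them, given any detection, in about half of cases at R²=0.15, a fifth at 0.20 and almost none at 0.30. The risk is greater in children and in lesional skin, and smaller at a looser threshold. Dropout by end of study would make the groups smaller still. These figures rest on an assumed threshold, assumed and equal R², and projected sizes; they describe a risk, not a forecast of the results. It also cannot be said that no criterion exists anywhere, because the Exploratory SAP was not available. The primary and secondary analyses are unaffected.

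**What to change.** In the Exploratory SAP, or by citing it if the rule is already there:

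- Call an eQTL outcome-group-specific only if a genotype-by-group interaction, or an effect-size heterogeneity test within the planned meta-analysis, passes FDR 5%. Use estimates and standard errors, not test statistics alone.
- Apply the same standard to endotypes by comparing endotype-high with endotype-low participants.
- List the other eQTLs as detected in group A, difference from other groups not shown. Give estimates and confidence intervals for every group with samples: five for non-lesional skin, four for lesional.

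No new data are needed, and the approach matches SO2 and EO14. The price is that few eQTLs will qualify as specific, since interaction and heterogeneity tests have limited power in groups of this size.

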	(dupilumab-naïve participants only) 18. Non-lesional and lesional skin biopsy endotypes determined in exploratory objective 4 (dupilumab-naïve adults only)	determined by skin endotype status.
12. To determine whether AD skin endotypes are associated with dupilumab response	19. Non-lesional and lesional skin tape endotypes determined in exploratory objective 4 (dupilumab-naïve participants only) 20. Non-lesional and lesional skin biopsy endotypes determined in exploratory objective 4 (dupilumab-naïve adults only)	12. The clinical response to dupilumab treatment will be determined by skin endotype status.
13. To determine whether cell type-specific gene and protein expression and cellular composition differ among AD skin endotypes	21. Single cell non-lesional and lesional skin biopsy transcriptome and proteome (adults only)	13. Shifts in the cellular composition of skin and cell type-specific gene and protein expression changes underlie skin endotypes.
14. To determine longitudinal changes in skin (skin tape) gene expression across standard-of-care treatment (all timepoints) in the study outcome groups: (1) topical steroid responders, (2) dupilumab responders, (3) dupilumab non-responders, (4) non-AD, and (5) long-term dupilumab participants	22. Non-lesional and lesional skin tape transcriptome	14. The clinical response to protocol's standard-of-care treatment among different AD participants will be associated with distinct transcriptional trajectories generated across these standard-of-care treatments.
15. To determine whether genetic variation that regulates skin gene expression is associated with AD disease	23. Non-lesional and lesional skin tape and skin biopsy transcriptome 24. Genome-wide genotypes from blood samples	15. Genetic variation drives particular AD skin endotypes.
16. To determine the proteomic profiles of AD lesional and non-lesional skin endotypes	25. Non-lesional and lesional skin tape proteome	16. AD skin endotypes exhibit distinct epidermal protein profiles.
17. To determine the lipidomic and metabolomic properties of AD lesional and non-lesional skin endotypes	26. Non-lesional and lesional skin tape lipidome and metabolome	17. AD skin endotypes exhibit distinct lipid and metabolome profiles.

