We will obtain WTS data to investigate transcriptional differences between naïve and long-term users of dupilumab. We will use a GLM to compare gene expression between naïve and long-term users at each visit separately.

The above tests will be performed separately for lesional and non-lesional skin and for children and adults, after which expression differences between naïve and long-term dupilumab users will be compared both between skin types and age cohorts.

Identifying novel AD skin endotypes at all skin sampling time points [EO #4]

Endotype identification analysis will be carried out using WTS data collected from non-lesional/lesional STS and non-lesional/lesional biopsy (adults only) samples at each of the sample time points. Separate analyses will be carried out for children and adults, for STS and biopsy samples, and for non-lesional and lesional skin.

There is no straightforward way to identify endotypes of complex disease. Therefore, we will employ a series of complementary approaches to identify participants with previously defined and novel disease endotypes, which we detail in the SAP. These approaches will either yield gene sets (based on previous studies, DE analysis, or WGCNA) or summary expression states (based on topic modeling; ([Dey et al, 2017](#)) that alone or in combination may capture distinct pathobiological mechanisms of disease.

For each gene set-based endotype identification analysis, we will derive a summary representation of the endotype by treating expression of each gene set as a continuous or a dichotomous variable, in turn. In the case of a continuous variable, we will calculate the geometric mean of expression across each functional gene set. In the case of a dichotomous variable, for each set of endotype genes, we will divide individuals into endotype-high and endotype-low expression categories by hierarchically clustering all participants into $K = 2$ groups based on gene-level expression.

Finally, for expression state-based endotype identification, all participants will be profiled based on their mixture of proportional expression across a range of expression states identified. These membership

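### EO15's additional endotype-high eQTL step selects participants on expression and has no comparator, so it cannot show that a variant acts specifically in an endotype, and it is weak for variants that drive a whole endotype

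*Protocol*

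**What the plan says.** The hypothesis attached to EO15 in Protocol Table 2.1.3 is "Genetic variation drives particular AD skin endotypes." The objective itself asks whether variants that regulate skin gene expression are associated with AD.

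Protocol 13.4.4 [EO #15] has four parts:

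1. A cis-eQTL analysis that is not restricted by endotype: "The eQTL analysis will be performed separately for children and adults, lesional and non-lesional skin, different visits, and different outcome groups." Strata are then pooled: "We will perform a meta-analysis of the test statistics for different sample groups."
2. A look-up of endotype genes, and of genes enriched in endotype-defining cell types, in those results.
3. An additional step: "we will perform eQTL analyses separately for the most common endotype groups", defined as analyses "for endotype-high individuals within endotypes with $n > 50$ high individuals." The conclusion drawn from it is "These analyses will identify genetic variants that affect gene expression specifically in AD endotype groups, which should be enriched for endotype genetic risk variants."
4. A TWAS of AD cases against healthy controls, built on the skin cis-eQTL data.

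For gene-set endotypes, EO4 sets the high and low groups as follows: "we will divide individuals into endotype-high and endotype-low expression categories by hierarchically clustering all participants into $K = 2$ groups based on gene-level expression." SAP 2.3 and 9.3 send all exploratory analyses to a separate Exploratory SAP, which is not among the documents.

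**The concern.** The third part makes a comparative claim, that an effect is specific to an endotype, from one arm of the comparison. An eQTL found among endotype-high people may be just as strong among endotype-low people, and nothing described would show the difference.

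The step also conditions on the outcome. A variant that drives an endotype does so by raising expression of the endotype genes, which moves carriers from low to high. Keeping only the high group removes most of that contrast. The null tested is no variant effect among people who are already high, which is not hypothesis 15.

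The protocol handles similar questions differently elsewhere. EO11 and EO12 model endotype status, high or low, across everyone analysed, with interaction terms. EO14 and Secondary Objective 2 also test interactions. Genotype is the exception.

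At stake is how EO15 is read: shared skin eQTLs could be reported as endotype-specific, and the stated enrichment for risk variants would have no support.

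**Working it through.** EO15 states no power, alpha or effect size, so it has no figure of its own to reproduce.

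**Inputs from the documents.** Dupilumab-naïve AD adults: 160 + 100 = 260 (Protocol 13.7.1). Endotype-high prevalence 50%, stated there for type 2-high and borrowed here, giving 130 high. Threshold of more than 50 high individuals (EO15). Alpha 0.05/10,000 = 5e-6, stated for Secondary Objective 1 and borrowed for some runs.

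**Assumptions not in the documents.** Minor allele frequency 0.3, additive effects, 20 or 30 endotype genes, endotype-high taken as the top scorers on mean endotype-gene expression, and the effect sizes below.

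**1. Shared eQTL, same effect in everyone.** With variance explained R², the Fisher approximation gives z = atanh(√R²) × √(n − 3), compared with 4.42 at two-sided p = 1e-5. For n = 130, √127 = 11.27.
- R² = 0.15: z = 0.409 × 11.27 = 4.60; power Φ(4.60 − 4.42), about 57%. Simulation: 56%.
- R² = 0.20: z = 0.481 × 11.27 = 5.42; power Φ(5.42 − 4.42), about 84%. Simulation: about 84-85%.

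These are the chances that a non-specific eQTL is significant in the endotype-high analysis. Calling an eQTL specific when it is significant in the high group and not in the low group does not cure this. At 5e-6, for R² of 0.1 and 0.2 with 130 or 200 high, that rule still mislabels shared eQTLs 2-27% of the time.

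**2. Variant driving the whole gene set.** Let endotype activity be L = 0.5 × G + N(0,1), with 30 genes loading 0.7 on L. The slope in everyone is 0.7 × 0.5 = 0.35. Selecting the upper half on a score correlated r with L multiplies the slope by about 1 − (2/π)r². Here Var(L) = 1 + 0.25 × 0.42 = 1.105 and r² = 0.541/(0.541 + 0.51/30) = 0.97. The factor is 1 − 0.637 × 0.97 = 0.38, and 0.35 × 0.38 = 0.13. Simulation gives 0.14.

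| Power at 0.05, N = 260 | All | Random half | Endotype-high half | Genotype vs high/low status, all |
|---|---|---|---|---|
| Loading 0.7 | 95% | 71% | 25% | 98% |
| Loading 0.5 | 75% | 45% | 14% | 97% |

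The random half separates the causes: 95% to 71% is sample size, and 71% to 25% is selection.

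**3. Variant acting in cis on one member gene.** With the same effect size, the slope is 0.35 in all and 0.34 in the high half. Power is about 95% in all, 71% in a random half and 85% in the high half, so there is almost no attenuation. The test of genotype against endotype status rejects about 5% of the time, which is right, because this variant does not drive the endotype.

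**4. What the rest of EO15 recovers.** Driver variants at alpha 5e-6 (20 genes, loading 0.7; R² is for the cis gene):

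| N / number high | R² | Meta-analysis over outcome groups | Endotype-high only | Genotype vs status, all |
|---|---|---|---|---|
| 400 / 200 | 0.1 | 98% | 8% | 68% |
| 400 / 200 | 0.2 | 100% | 59% | >99% |
| 260 / 130 | 0.1 | 79% | 3% | 28% |
| 260 / 130 | 0.2 | 100% | 24% | 91% |

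With 51 high of 260, just above the protocol's threshold, endotype-high power is at most 1% for every R² from 0.05 to 0.3.

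**5. Behaviour of an interaction test at 0.05.** For shared eQTLs in genes unrelated to the endotype it is positive 4-6% of the time, as it should be. For drivers with a uniform true effect it is positive 5-11% of the time at a 50:50 split, and 15-50% with 51 high of 260, because the groups are defined by expression.

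**The case against.** A reader might infer that EO15 searches for variants only inside endotype-high participants, so that real drivers are mostly lost. The documents do not support that. The step is introduced as an addition to a cis-eQTL analysis not restricted by endotype, and there is also a meta-analysis, an endotype-gene look-up and a TWAS. The fourth check shows that the meta-analysis would find the same drivers as skin eQTLs.

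Other points on the plan's side:

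- **The objective concerns AD disease, which the TWAS addresses.** True of the objective, but hypothesis 15 is about endotypes. The look-up asks whether endotype genes have eQTLs, and the TWAS contrasts AD with controls. Neither tests whether a variant moves people into an endotype.
- **A cis-eQTL usually acts on one gene, where attenuation is negligible.** This stands. The loss in the endotype-high step applies when the variant, or its cis gene, moves the whole set.
- **No list of endotype-specific eQTLs is defined.** The outputs named are general and outcome-group-specific eQTLs, so a formal mislabelled list cannot be assumed. The sentence claiming specificity is still in the protocol.
- **The split is simplified.** EO4 clusters rather than cutting at the median, and has a second route through expression-state membership. The attenuation figures illustrate the gene-set route only.
- **The Exploratory SAP may supply a comparator.** It may. The protocol sentence would still need to agree with it.

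**Conclusion.** The point holds for the endotype-high step. As described, it cannot show that an eQTL acts specifically in an endotype, and the expected enrichment for endotype risk variants is unsupported. A shared eQTL explaining 15-20% of variance would be significant there about 56-85% of the time (130 people, p<1e-5). The step is weak for whole-set drivers (slope 0.35 to 0.14; power 95% in all, 71% in a random half, 25% in the high half), but not for variants acting on a single member gene.

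The point does not extend to EO15 as a whole, whose unrestricted analyses would still detect drivers as skin eQTLs. What the available text lacks is a test linking genotype to endotype status.

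The sizes depend on assumed allele frequency, loadings, effect sizes and a 50:50 split. The missing comparator does not depend on them. EO15 is exploratory, and the primary and secondary analyses are unaffected.

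**What to change.** In Protocol 13.4.4 [EO #15], and in the Exploratory SAP if it does not already do so:

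1. In all AD participants, within the planned strata, test genotype against endotype status (high versus low) and against the continuous endotype score. Make this the lead test of hypothesis 15.
2. For lead eQTLs, call an effect endotype-specific only if a genotype × endotype interaction passes FDR 5%. Do not apply the label to variants in endotype-defining genes or to variants associated with endotype status, because selection on expression can bias the interaction there.
3. Replace the sentence claiming that the endotype-high analyses will identify endotype-specific variants with one saying that they are descriptive.

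The cost is some additional analysis of genotypes and endotype calls the study already plans to hold; no new data are needed. Few interactions are likely to reach significance at this sample size, and the text should say so.
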